4.1.4 Period 2 (Multiple-ascending-dose Period)

Period 2 will not be initiated until this Substantial Amendment to the IMPD with the supportive nonclinical data is approved by the local regulatory authorities. Following this approval, the Sponsor intends to initiate Period 2. The Sponsor will communicate this approval (in writing) directly to the study sites.

the DEC/SMC recommended that Period 2 can initiate at a dose level of 30 mg Q8W.

4.1.4.1 *Period 2 Assessment of Continued Patient Eligibility*

Before initiation of Period 2, the Investigator should confirm patient eligibility to continue in the study ([Section 4.2](#)). If any clinically significant medical findings are observed that, in the judgment of the Investigator (and in consultation with the Sponsor), would make the patient unsuitable for continued participation in the study and/or completion of the study procedures, the patient may not be allowed to participate in Period 2. Applicable evaluations and tests from the last in-clinic visit in Period 1 may be used if the last in-clinic visit occurred within 4 weeks prior to the Confirm Eligibility visit for Period 2. Patients who are considered eligible and have completed at least through Period 1 Week 12/Day 85 may participate in Period 2. New patients will be screened for eligibility.

4.1.4.2 *Period 2 Treatment Assignment*

Patients in P2C1 will receive 30 mg WVE-003 or placebo administered Q8W. Approximately 24 patients will be enrolled in P2C1. Dose levels and cohort sizes for Period 2 subsequent cohorts will be determined by the DEC/SMC, based on previous Period 2 cohort data. Doses will be administered no more often than Q8W through Week 16 (maximum of 3 doses). █

All patients from Period 1 will have the opportunity to roll into Period 2 and will receive up to 3 additional doses of WVE-003 or placebo. Patients will not be re-randomized and will continue to receive active drug or placebo based on Period 1 treatment assignment. Patients will roll into the current Period 2 cohort, irrespective of Period 1 dose level.

Patients may be replaced in accordance with the requirements for dose escalation. Future DEC/SMC recommendations may include the addition of new Period 2 patients. All new patients in Period 2 will receive up to 3 doses of WVE-003 administered no more often than Q8W.

4.1.4.3 *Period 2 Treatment*

Within 1 week prior to performing any lumbar puncture, a blood sample will be tested locally for platelet count and prothrombin time to confirm that it is safe to proceed with the lumbar puncture. Other predose assessments may also be performed up to 1 week prior to dosing as specifically listed in [Table 3](#) including UHDRS, PBA-s, and weight.

The Period 2 MAD cohorts will be conducted in a sequential manner. Subsequent multiple-dose cohorts will not initiate until the criteria for dose escalation are met ([Section 4.4.1.3](#)).

Immediately after study drug administration in any cohort, all patients should be ambulatory and active for approximately 30 minutes postdose on all dosing days. The Investigator should note any weakness or fatigue during this period. Formal physical examinations targeting the neurological system will be performed postdose at the time points specified in [Table 3](#).

Patients will attend clinic visits Q4W for assessments of safety, PK, and PD. Patients in P2C1 will receive doses on Week 0, Week 8, and Week 16. Pending DEC/SMC recommendation, subsequent cohorts may receive doses Q8W or less frequently (e.g., on Week 0 and Week 12).

4.1.4.4 *Period 2 Follow-up*

All patients are required to complete follow-up assessments, including evaluations of safety, PD, PK, clinical effects, and MRI. Patients will be followed up for a minimum of 12 weeks after the last dose. Any postdose SAEs will be monitored until resolution.

4.1.5 *Early Termination Visit*

If a patient withdraws from the study early, the patient should complete an early termination visit. Refer to [Section 5.3](#) for information on early withdrawal from study drug or from the study.

4.2 Schedule of Assessments

The schedule of assessments for Period 1 is presented in [Table 1](#). Detailed time points for select assessments in Period 1 are provided in [Table 2](#).

The schedule of all assessments for Period 2 is presented in [Table 3](#). Detailed time points for select assessments in Period 2 are provided in [Table 4](#).

Of note, specific instructions regarding COVID-19 considerations, are provided in [Section 4.4.5](#).

Table 1 Schedule of Assessments (Period 1)

	Pre-screening ^a	Screening ^b	Double-blind Treatment (Single Dose)		Sentinel Patient Follow-up	Required Follow-up				Additional Follow-up Visits			ET
			3	4		6	7	8	9	10*	11*	12*	
Visit	1	2	3	4	5	6	7	8	9	10*	11*	12*	
Week		-4 to 0	0	0	0	2	4	8	12	16	20	24	
Study Day (Visit Window, if applicable)		Day -28 to -1	Baseline (Day -6 to Day 1) ^c	Dosing (Day 1)	D2 (24 ± 4 h postdose)	D3 (48 ± 4 h postdose)	D15 (±2)	D29 (±2)	D57 (±3)	D85 (±5)	D113 (±5)	D141 (±5)	D169 (±5)
Event/Assessment			X ^c										
Study drug administration via IT injection ^j													

Abbreviations: 3T = 3 Tesla; A = adenine; AE = adverse event; CAG = cytosine-adenine-guanine; CSF = cerebrospinal fluid; C-SSRS = Columbia-Suicide Severity Rating Scale; D = day; ECG = electrocardiogram; EOS = end of study; ET = early termination; h = hour; HBsAg = hepatitis B surface antigen; HCV = hepatitis C virus; ICF = informed consent form; IT = intrathecal; LP = lumbar puncture; MRI = magnetic resonance imaging; PBA-s = Short Problem Behaviors Assessment; PBMC = peripheral blood mononuclear cell; PD = pharmacodynamic(s); PK = pharmacokinetic(s); PT = prothrombin time; SNP = single nucleotide polymorphism; SNP3 = SNP rs362273; UHDRS = Unified Huntington's Disease Rating Scale; W = week.

* Visits on W16, W20, and/or W24 only need to be completed if the multiple-dose portion (Period 2) of the study has not initiated by the time the patient has reached W12/D85. At any point after W12/D85, the patient may roll over to Period 2 once initiated. Any patient who completes W12/D85 may be asked to return for the next applicable visit according to their number of days postdose. If a patient is past W24/D169, they may be asked to return for the assessments outlined on the W24/D169 visit.

^a Prescreening must be performed to confirm heterozygosity at SNP3 with the A variant only on the same allele as the CAG triplet expansion. Prescreening can happen any time before Screening. It is anticipated that it will take up to 6 weeks to process the results of this testing.

^b Screening assessments can occur on multiple days, provided they are within the 4-week Screening period.

^c Noted predose/baseline procedures must be performed within 24 hours predose. All others can be performed up to 1 week prior to dosing. Postdose procedures should be performed as described for each assessment.

^d The UHDRS, PBA-s, and C-SSRS should be completed prior to any other assessments.

^e Physical examination includes (at a minimum) the head, eyes, ears, nose, and throat, as well as the respiratory, cardiovascular, gastrointestinal, musculoskeletal, psychiatric, and neurologic systems. Predose physical examination should be done on Day 1 prior to dosing.

^f Targeted postdose physical examination to assess potential motor effects focuses on the neurologic system, with special attention to the motor system, upper and lower extremity measures of strength, tone, reflexes, and ambulation. This should be performed at 1 and 4 hours postdose (±15 minutes) on Day 1.

^g Blood pressure (systolic and diastolic) and pulse will be measured ≤60 minutes predose and 4 hours (±15 minutes) postdose on Day 1 and once at all other noted visits. Patient must rest quietly for ≥3 minutes prior to measuring.

^h Negative serum pregnancy test will be documented at Screening for female patients. Negative urine pregnancy test will be documented predose for female patients on Day 1.

ⁱ Blood sample will be tested locally for platelet count and prothrombin time pre-LP to confirm safe to proceed with the lumbar puncture.

^j Immediately after study drug administration, patients should be active for approximately 30 minutes postdose.

^k All patients will remain in the clinic and have AEs and concomitant medications recorded through 1 day postdose. In addition, 2 sentinel patients will remain in the clinic and have AEs and concomitant medications recorded throughout the 2-day postdose period.

¹ This assessment will be performed only if optional lumbar puncture is performed at ET.

Table 2 Detailed Time Points for Selected Assessments (Period 1)

Assessments	Screening	D1										D2	Sentinel Patient Fol/up D3	W2 (D15)	W4 (D29)	W8 (D57)	W12 (D85)	W16 (D113), W20 (D141)*	W24 (D169)*	ET										
		Pre-dose	Postdose																											
			30 m	1 h	2 h	4 h	6 h	0 to 4 h	4 to 8 h	8 to 24 h	24 h																			
Window (±)		4 h	5 m	15 m	15 m	30 m	30 m	2 h	2 h	2 h	2 h	4 h	2 d	2 d	3 d	5 d	5 d	5 d												
CSF sample ^a		X													X	X	X	X				X ^b								
Plasma PD		X													X	X	X	X	X	X	X	X								
Plasma PK		X	X	X	X	X	X					X			X	X	X	X				X								
Urine PK								X	X	X																				
PBMC sample for biomarker analyses		X										X			X	X	X	X		X	X									
ECG ^c	X	X		X	X	X					X								X	X	X									
Serum sample for Immunogenicity		X															X					X								
Clinical laboratory tests (full panel) ^d	X	X														X					X	X								
Clinical laboratory tests (CBC, CRP, complement, and fibrinogen)				X		X						X		X																

Abbreviations: CBC = complete blood count; CRP = C-reactive protein; CSF = cerebrospinal fluid; D = day; ECG = electrocardiogram; ET = early termination; h = hour; m = minute; PBMC = peripheral blood mononuclear cell; PD = pharmacodynamic(s); PK = pharmacokinetic(s); W = week.

*Visits on W16, W20, and/or W24 only need to be completed if the multiple-dose portion (Period 2) of the study has not initiated by the time the patient has reached W12/D85. At any point after W12/D85, the patient may roll over to Period 2 once initiated. Any patient who completes W12/D85 may be asked to return for the next applicable visit according to their number of days postdose. If a patient is past W24/D169, they may be asked to return for the assessments outlined on the W24/D169 visit.

^a On Day 1, CSF sample will be collected approximately 15 minutes prior to study drug administration. At all noted time points, approximately 20 mL of CSF total should be collected. CSF samples must be tested locally for safety for the following parameters: total protein, glucose, and cell counts (white blood cell counts with differential) on all noted visits.

^b This lumbar puncture is optional for patients who terminate early.

^c Electrocardiogram recordings will be obtained in triplicate in the supine position after the patient has rested comfortably for ≥ 10 minutes. ECGs should be performed in triplicate. At time points when plasma PK is also being collected, the ECG should be performed first, and PK should be collected within 30 minutes after (and within the applicable postdose window).

^d Parameters to be assessed are detailed in [Table 6](#). Clinical laboratory safety baseline assessments will be performed up to 1 week prior to dosing. Note that these assessments also include CBC, CRP, complement, and fibrinogen.

Table 3 Schedule of Assessments (Period 2)

Visit	New Patients Only		Rollover Patients	Double-blind Treatment ^c (Repeat Dose)						Follow-up			ET
	Pre-screening ^a	Screen-ing ^b	Confirm Eligibility	3	New Patients Only	5	6	7	8	9	10	11 (EOS)	
						4							
Week	-4 to 0		-4 to 0	0		4	8	12	16	20	24	28	
Study Day (Visit Window, if applicable)	Day -28 to -1	Day -28 to -1	Baseline (Day -6 to Day 1)	Dosing (Day 1)	D2 (24 ± 4 h postdose)	D29 (±3)	D57 (±3)	D85 (±3)	D113 (±3)	D141 (±3)	D169 (±3)	D197 (±5)	ET
Adverse event monitoring		X	X	X ^{c,l}	X ^l	X ^c	X ^c	X ^c	X ^c	X	X	X	X
Pre-LP PT and platelet ^j				X		X	X	X	X	X	X	X	X ^m
12-lead ECG	X	X		X ^p		X	X	X	X	X			X
Clinical laboratory tests	X	X	X	X ^p	X ^p	X ^p	X ^p	X ^p	X ^p	X ^p	X ^p	X ^p	X ^p
Blood sample for PK and PD				X ^p	X ^p	X ^p	X ^p	X ^p	X ^p	X ^p	X ^p	X ^p	X ^p
Serum sample for immunogenicity				X ^p		X ^p							
CSF sample for safety, drug concentration, and PD				X ^p		X ^p							
PBMC sample for biomarker analyses				X ^p	X ^p	X ^p	X ^p	X ^p	X ^p		X ^p	X ^p	
3T MRI of the brain (without contrast)		X		X ⁿ							X		

Visit	New Patients Only		Rollover Patients	Double-blind Treatment ^c (Repeat Dose)						Follow-up			ET
	Pre-screening ^a	Screen-ing ^b	Confirm Eligibility	3	New Patients Only	5	6	7	8	9	10	11 (EOS)	
						4							
Week	-4 to 0		-4 to 0	0		4	8	12	16	20	24	28	
Study Day (Visit Window, if applicable)				Baseline (Day -6 to Day 1)	D2 (24 ± 4 h postdose)	D29 (±3)	D57 (±3)	D85 (±3)	D113 (±3)	D141 (±3)	D169 (±3)	D197 (±5)	
Event/Assessment	Day -28 to -1	Day -28 to -1		Dosing (Day 1)									
Study drug administration via IT injection ^k			X ^c			Dosing visits only ^c							
Study completion												X	X

Abbreviations: 3T = 3 Tesla; A = adenine; AE = adverse event; CAG = cytosine-adenine-guanine; CSF = cerebrospinal fluid; C-SSRS = Columbia-Suicide Severity Rating Scale; D = day; ECG = electrocardiogram; EOS = end of study; ET = early termination; h = hour; HBsAg = hepatitis B surface antigen; HCV = hepatitis C virus; ICF = informed consent form; IT = intrathecal; LP = lumbar puncture; MRI = magnetic resonance imaging; PBA-s = Short Problem Behaviors Assessment; PBMC = peripheral blood mononuclear cell; PD = pharmacodynamics; PK = pharmacokinetics; PT = prothrombin time; SNP = single nucleotide polymorphism; SNP3 = SNP rs362273; UHDRS = Unified Huntington's Disease Rating Scale.

- ^a Prescreening must be performed to confirm heterozygosity at SNP3 with the A variant only on the same allele as the CAG triplet expansion. Prescreening can happen any time before Screening. It is anticipated that it will take up to 6 weeks to process the results of this testing.
- ^b Screening assessments can occur on multiple days, provided they are within the 4-week Screening period.
- ^c Noted assessment must be performed within 24 hours predose. All others can be performed up to 1 week prior to dosing. Postdose procedures should be performed as described for each assessment.
- ^d The UHDRS, PBA-s, and C-SSRS should be completed prior to any other assessments.
- ^e Weight and temperature will be collected predose on dosing days and once at all other noted time points.
- ^f Physical examination includes (at a minimum) the head, eyes, ears, nose, and throat, as well as the respiratory, cardiovascular, gastrointestinal, musculoskeletal, psychiatric, and neurologic systems. Predose physical examination should be done on the day of dosing.
- ^g Targeted postdose physical examination to assess potential motor effects focuses on the neurologic system, with special attention to the motor system, upper and lower extremity measures of strength, tone, reflexes, and ambulation. This should be performed at 1 and 4 hours postdose (±15 minutes) on all dosing days.
- ^h Blood pressure (systolic and diastolic) and pulse will be measured ≤60 minutes predose and 4 hours (±15 minutes) postdose on dosing days and once at all other noted visits. Patient must rest quietly for ≥3 minutes prior to measuring.
- ⁱ Negative serum pregnancy test will be documented at Screening for new female patients in Period 2. Negative urine pregnancy test will be documented predose for female patients on dosing days.
- ^j Blood sample will be tested locally for platelet count and prothrombin time up to 1 week prior to any LP to confirm safe to proceed with the lumbar puncture.
- ^k Immediately after study drug administration, patients who are able should be active for approximately 30 minutes postdose. If the DEC decides to reduce dose frequency or number of doses (Section 4.4.1.3), patients will complete all study assessments at the noted visits, but may not receive study drug.
- ^l All patients will remain in the clinic and have AEs and concomitant medications recorded through 1 day postdose.

- ^m This assessment will be performed only if optional lumbar puncture is performed at ET.
- ⁿ This MRI should be performed for rollover patients only. If the Period 1 Week 24/Day 169 visit was conducted <4 weeks prior to the Period 2 Day 1 visit, the MRI does not need to be repeated.
- ^o Assessments from the last in-clinic visit in Period 1 may be used if the last in-clinic visit occurred within 4 weeks prior to the Confirm Eligibility visit for Period 2.
- ^p Reference [Table 4](#) for details regarding assessments and time points.

Table 4 Detailed Time Points for Selected Assessments (Period 2)

Assessment	New Patients Only	Roll-over Patients	D1							New Patients Only	W4 (D29)	W8 (D57)		W12(D85) and W16 (D113)						W20 (D141)	W24 (D169)	W28 (D197)	ET					
	Screening	Confirm Eligibility										D2	Pre-dose	Postdose (Dosing Visit Only)	Pre-dose	Postdose (Dosing Visit Only)												
	30 m	1 h										2 h	4 h	6 h														
	4h	5 m	15 m	15 m	30 m	30 m	2h	2h	1 h	4 h	5 m	15 m	15 m	30 m	30 m	3 d	3 d	3 d										
Window (±)																												
CSF sample ^a					X								X	X		X							X	X	X	X ^b		
Plasma PD					X								X	X		X							X	X	X	X		
Plasma PK					X	X	X	X	X	X		X	X		X		X	X	X	X	X	X	X	X	X			
PBMC sample for biomarker analyses					X							X	X	X		X										X		
ECG ^c	X ^e				X		X	X	X			X				X		X				X				X		
Serum sample for immunogenicity					X								X	X		X							X	X	X	X		
Clinical laboratory tests (full panel) ^d	X ^e	X ^e	X									X	X		X							X	X	X	X			
Clinical laboratory tests (CBC, CRP, complement, fibrinogen)						X		X				X																

Abbreviations: CBC = complete blood count; CRP = C-reactive protein; CSF = cerebrospinal fluid; D = day; ECG = electrocardiogram; ET = early termination; h = hour; m = minute; PBMC = peripheral blood mononuclear cell; PD = pharmacodynamic(s); PK = pharmacokinetic; W = week.

^a Predose on all dosing days, CSF sample will be collected approximately 15 minutes prior to study drug administration. At all noted time points, approximately 20 mL of CSF total should be collected. CSF samples must be tested locally for safety for the following parameters: total protein, glucose, and cell counts (white blood cell counts with differential) on all noted visits.

^b This lumbar puncture is optional for patients who terminate early.

- Electrocardiogram recordings will be obtained in the supine position after the patient has rested comfortably for ≥ 10 minutes. At time points when plasma PK is also being collected, the ECG should be performed first, and PK should be collected within 30 minutes after (and within the applicable postdose window).
- Parameters to be assessed are detailed in [Table 6](#). Clinical laboratory safety assessments will be performed up to 1 week prior to dosing on all dosing days. Note that these assessments also include CBC, CRP, complement, and fibrinogen.
- Assessments from the last in-clinic visit in Period 1 may be used if the last in-clinic visit occurred within 4 weeks prior to the Confirm Eligibility visit for Period 2.

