Period 1 Urine PK: Samples will be collected on Week 0/Day 1 from 0-4 hours, 4-8 hours, and 8-24 hours postdose.

Period 1 CSF PK: Samples will be collected predose on Week 0/Day 1, as well as Week 2, Week 4, Week 8, and Week 12. A sample will also be collected at the ET visit, if the patient discontinues early.

Period 2 Plasma PK: At the first and last dosing visit, blood samples will be collected predose (within 4 hours prior to dosing), and postdose at 30 minutes (± 5 minutes), 1 hour (± 15 minutes), 2 hours (± 15 minutes), 4 hours (± 30 minutes), and 6 hours (± 30 minutes). New patients only will also have a sample collected on Day 1 at 24 hours (± 2 hours) postdose. For any other dosing visit, blood samples will be collected at 2 hours (± 1 hour) postdose. In addition, plasma PK samples will be collected once at all non-dosing clinic visits. A sample will also be collected at the ET visit, if the patient discontinues early.

Period 2 CSF PK: Samples will be collected at all clinic visits (Week 0/Day 1, Week 4, Week 8, Week 12, Week 16, Week 20, Week 24, and Week 28). The sample will be collected predose on dosing visits. A sample will also be collected at the ET visit, if the patient discontinues early.

The date and time of the sample collection will be recorded.

Samples will be analyzed by a central laboratory to determine concentrations of WVE-003 using validated methods (plasma and CSF) or qualified methods (urine).

Samples will only be used by the Sponsor and/or a contracted vendor for research related to the development of treatments for HD and stored for a maximum of 10 years. All biological material will be stored and secured in a way that ensures that unauthorized access is prohibited and the samples are not lost, deteriorated, or destroyed accidentally or illegally. Detailed instructions for sample collection, storage, processing, and shipping will be provided in the Laboratory Manual.

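### In Period 2 the acute blood panel (CBC, CRP, complement, fibrinogen) follows only the first dose, so transient, silent laboratory changes after the Week 8 and Week 16 doses are not captured

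*Combined protocol and SAP*

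**What the plan says.** Dosing and visits (protocol section 4.1.4): "Patients in P2C1 will receive doses on Week 0, Week 8, and Week 16". On cohort size, "Approximately 24 patients will be enrolled in P2C1". On visits, "Patients will attend clinic visits Q4W for assessments of safety, PK, and PD".

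Table 4 (Period 2) has two laboratory rows.

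- The short panel, "Clinical laboratory tests (CBC, CRP, complement, fibrinogen", has three marks: two early post-dose times on Day 1, and Day 2, a column for new patients only. No mark falls in the post-dose columns for Week 8 or for Weeks 12 and 16.
- The full panel is marked at eligibility, before the dose on dosing days, at the 4-weekly visits between and after doses, and at early termination. Its footnote says "Clinical laboratory safety assessments will be performed up to 1 week prior to dosing on all dosing days" and adds "Note that these assessments also include CBC, CRP, complement, and fibrinogen".

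Section 8.2.7 leaves the timing of the short panel to the schedule and adds no draw. In Period 1 (Table 2) the corresponding row, "Clinical laboratory tests (CBC, CRP, complement, and fibrinogen", has four post-dose marks after the single dose.

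Post-dose blood is already taken later in Period 2 for another purpose. For plasma drug levels, section 8.3 states: "At the first and last dosing visit, blood samples will be collected predose (within 4 hours prior to dosing), and postdose at 30 minutes", with further draws to 6 hours.

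**The concern.** Safety and tolerability is the primary objective, and Period 2 is the repeat-dose part of the study. Its acute laboratory sampling is concentrated on the first Period 2 dose and is not resumed at the second or third. The documents give no reason.

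Three uses of the data depend on this sampling. Under section 4.4.1.3, the Dose Escalation Committee reviews safety once 6 patients have had two consecutive doses, but the schedule gives it no acute panel from the second Period 2 dose. Section 5.3.2 bases treatment interruption partly on platelet and inflammatory values, and no scheduled draw would reveal a short-lived change after dose 2 or 3. By-visit laboratory tables could show an acute shift only around Day 1, and a reader could take the absence of measurement at Weeks 8 and 16 for absence of effect. The plan follows anti-drug antibodies through Period 2, so responses to re-exposure are plainly of interest.

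**Working it through.** The plan gives no figure to reproduce; section 11.1 states that the sample size does not rest on hypothesis testing.

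**Placing the marks.** The column alignment of Table 4 is imperfect in the readable text, so the short-panel row was compared with the plasma PK, PBMC and CSF rows, the PK text in section 8.3 and the laboratory row of Table 3. The last short-panel mark lines up with Day 2. Table 3 shows laboratory tests at Day 2 and the full-panel row has none there, which agrees. Some rows are displaced by one or two cells, but even a two-cell shift would put that mark at Week 8 predose, not in a post-dose column for dose 2 or 3. The exact Day 1 hours cannot be fixed, and the finding does not depend on them.

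**Coverage in P2C1 (Period 2 Cohort 1).** About 24 patients × 3 doses = 72 administrations. About 24 have an acute panel; 72 − 24 = 48 (48/72 = 67%) have none.

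**Gap to the next scheduled panel** (visit days and windows from Table 3)

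- Dose 2, Day 57 ± 3, to Week 12, Day 85 ± 3: 85 − 57 = 28 days; range 28 − 6 = 22 to 28 + 6 = 34.
- Dose 3, Day 113 ± 3, to Week 20, Day 141 ± 3: 141 − 113 = 28 days; range 22 to 34.
- The local platelet count before a lumbar puncture may be taken up to 1 week earlier, so platelets could be checked from about 28 − 7 = 21 days.

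**Rollover patients.** They keep their Period 1 assignment (section 4.1.4.2) and enter at least 12 weeks after their Period 1 dose (section 2). For an active rollover patient, Period 2 Day 1 is already a re-exposure. The two Day 1 draws apply to them; the Day 2 draw does not.

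The rollover share is not stated. Section 2.3 plans 18 + 18 + 12 = 48 patients in Period 1, against about 54 in total (section 5). If both figures held, about 54 − 48 = 6 would be new, so at least 24 − 6 = 18 of P2C1 would be rollovers; at 2:1 that is 12 active.

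**Chance of seeing at least one event that occurs only on re-exposure.** Assumptions: 16 of 24 active (2:1; the Period 2 ratio is not stated), risk p per re-exposure, independent doses, and every event detected when a panel is drawn. With r active rollovers, P = 1 − (1 − p)^r as planned. If the last dosing visit is covered, P = 1 − (1 − p)^(r + 16).

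| p | r = 0: planned / with fix | r = 12: planned / with fix | r = 16: planned / with fix |
|---|---|---|---|
| 2% | 0% / 28% | 22% / 43% | 28% / 48% |
| 5% | 0% / 56% | 46% / 76% | 56% / 81% |
| 10% | 0% / 81% | 72% / 95% | 81% / 97% |

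For example, 1 − 0.95^12 = 46% and 1 − 0.95^28 = 76%. The figures with the fix are somewhat generous: they treat two draws as full acute coverage of the dose.

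**The case against.** The strongest defence is that heavy sampling at the first dose, followed by predose and 4-weekly panels, is a reasonable taper. Acute panels were taken after single doses up to 90 mg in Period 1, section 2.1 reports an acceptable safety profile, and the Period 2 regimen was chosen with limited accumulation in mind. That makes the schedule defensible as a choice and lowers the urgency. It does not supply acute laboratory data under repeat dosing, and the documents do not offer it as the reason.

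The defence also rules out three stronger readings that a reader might infer.

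- That acute reactions to doses 2 and 3 go unmeasured. They do not: neurological examination at 1 and 4 hours and blood pressure and pulse at 4 hours apply on every dosing day, and adverse events are recorded throughout. ECG marks also appear in the Week 12/16 post-dose block of Table 4. Sustained changes would show in the full panels.
- That nothing occurring only on re-exposure could be detected. This fails for rollover patients, who may be most of P2C1.
- That the schedule conflicts with section 11.3.4.2. That section promises summaries for each visit or assessment, not acute sampling after every dose.

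It is also fair to say that the choice of monitoring times is partly a clinical matter, and that adding only the last dosing visit leaves dose 2 uncovered.

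**Conclusion.** The gap is real but narrow, and it is an opportunity for a cheap improvement rather than an error. What is missed is a transient, clinically silent change in CBC, CRP, complement or fibrinogen after the second and third Period 2 doses, about two thirds of planned P2C1 administrations. New patients have no acute panel after any repeat dose; rollover patients have two draws after one re-exposure, at an interval of at least 12 weeks rather than 8.

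At an assumed 5% risk on re-exposure only, the chance of seeing at least one event as planned is 0% to 56%, and about 46% if 12 active patients are rollovers. The percentages rest on the assumed risk, the 2:1 allocation, independence between doses and the unknown rollover share. The absence of an acute panel after doses 2 and 3 rests only on Table 4 and its footnote, subject to checking the original columns.

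**What to change.** Confirm the short-panel columns in the original Table 4. If they are as read here, amend the table so that the short panel is also run on the post-dose PK draws already scheduled at the last dosing visit (Week 16 in P2C1), at the hours used on Day 1. Summarise change from that visit's predose value by dose number and arm.

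The cost is extra tubes and central laboratory analysis plus a minor amendment; no new visit or venepuncture is needed. Two limits remain: dose 2 stays uncovered, and without a 24-hour draw a later-peaking change may still be missed.

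If the sponsor keeps the present schedule, it should give the reason, and the study report should say that acute laboratory effects of doses 2 and 3 were not assessed.
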